Optimum Time for Extracorporeal Shock Wave Lithotripsy for Residual Stones after Percutaneous Nephrolithotomy: A Prospective Comparative Randomized Study

Protocol ID: FMBSUREC/02122025/[name]

Date: December 2, 2025

Introduction

Percutaneous nephrolithotomy (PCNL) is considered the gold standard for the treatment of large renal stones (1). However, residual fragments (RFs) are not uncommon, occurring in 10–30% of cases (2). Management of these fragments is essential, as they may serve as a nidus for recurrent stone formation, infection, or obstruction (3).

Extracorporeal shock wave lithotripsy (ESWL) is often used for treating such residual stones, yet there is no consensus regarding the optimal timing of ESWL following PCNL (4,5). Early ESWL may facilitate stone clearance before fragments become embedded or encrusted but might increase the risk of bleeding or infection due to incomplete renal healing. Conversely, delayed ESWL allows for better renal recovery but may permit stone growth or recurrent symptoms (4,6).

This study aims to determine the optimal timing of ESWL after PCNL to achieve the highest stone-free rate with minimal complications.

Aim of the Work

Primary Objective:

To compare stone-free rates between early and delayed ESWL after PCNL.

Secondary Objectives:

To compare complication rates between the two groups.

Methodology

Type of the Study:

Prospective, randomized, comparative clinical study.

Site of the Study:

Urology Department, Beni-Suef University Hospital.

Duration of the Study:

From December 2025 till December 2026.

Study Population:

Patients who underwent PCNL and were found to have residual renal stones ≤ 15 mm on postoperative imaging (CT or ultrasound).

Sample Size Technique:

Random consecutive sampling based on eligibility.

Sample Size Calculation:

Using Chi-square test to detect a 10% difference in stone-free rate (SFR) between groups.

Based on prior data showing $\text{SFR} \approx 93\text{--}95\%$.

Required sample:

214 patients per group at 90% power, $\alpha = 0.05$.

After adding 10% dropout:

238 patients per group \rightarrow Total sample size = 476 patients.

Inclusion Criteria:

- Age 18–70 years.
- Single or multiple residual renal stones ≤ 15 mm after PCNL.
- Normal renal function (serum creatinine < 1.5 mg/dL).
- No active UTI.

Exclusion Criteria:

- Bleeding disorders or anticoagulant therapy.
- Obstructed drainage or active sepsis.
- Stones > 15 mm or requiring secondary PCNL.

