Study Procedures / Tools:

Randomization:

Patients will be assigned into two equal groups: Total number of patients 476 patients and will be randomized to 238 patients per group →

Group A (Early ESWL): ESWL within 7–14 days after PCNL.

Group B (Delayed ESWL): ESWL after 3–4 weeks.

ESWL Protocol:

Same lithotripter model for all patients.

Sedation as needed.

Standardized energy and frequency according to EAU guidelines.

Maximum of 3 sessions.

Follow-Up:

Ultrasound or CT 2 weeks after final ESWL session.

Stone-free status = no fragments >2 mm.

Outcome Measures:

Primary:

Stone-free rate at 3 months.

Secondary:

Complications (hematuria, fever, infection).

Pain score (VAS).

Need for secondary intervention (URS or PCNL).

Statistical Analysis:

SPSS version 26.

Continuous variables: mean \pm SD, Student's t-test.

Categorical variables: percentages, Chi-square test.

$P < 0.05$ considered significant.

Ethical Consideration:

The study protocol will be reviewed and approved by the Research Ethics Committee, Faculty of Medicine, Beni-Suef University before conducting the study.

Sufficient time will be allocated to each patient and their family to explain the procedure in detail, including discussions with other patients who have previously undergone the same procedure.

A comprehensive explanation of the research project will be provided to all participants prior to enrolment.

Written informed consent will be taken from all study participants before enrolment in the study.

The study followed the Declaration of Helsinki for research ethics standards.

References:

2. El-Nahas AR, et al. J Urol. 2012;187(5):1673–1677.
3. Tefekli A, et al. Eur Urol. 2008;53(1):184–190.
4. Diri A, et al. Urolithiasis. 2018;46(3):281–287.
5. Türk C, et al. EAU Guidelines on Urolithiasis. 2024.
6. Abdelhafez MF, et al. World J Urol. 2021;39(6):1827–1836.
7. Desoky et al. Arab J Urol. 2017;15:20–35.

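### The primary endpoint is dated 3 months from no stated origin, while the only scheduled outcome scan follows the last ESWL session by two weeks; the two do not agree

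*Protocol*

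**What the plan says.** The relevant text is all in the Protocol, under Study Procedures / Tools and Outcome Measures.

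- Primary outcome (Outcome Measures): "Stone-free rate at 3 months". It is not said whether the 3 months run from PCNL, randomisation, the first ESWL session or the last.
- Imaging (Follow-Up): "Ultrasound or CT 2 weeks after final ESWL session". No other follow-up scan or visit is scheduled anywhere in the document.
- Definition of the outcome, on the line below that scan: "Stone-free status = no fragments >2 mm". It makes no reference to 3 months.
- Timing of treatment (Randomization): Group A has "ESWL within 7–14 days after PCNL". For Group B the text is "Group B (Delayed ESWL): ESWL after 3–4 weeks", with no origin repeated.
- Number of sessions (ESWL Protocol): "Maximum of 3 sessions". The interval between sessions is not given.

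**The concern.** The outcome line and the follow-up schedule describe two different measurements. One is a status at a calendar time point. The other is a status at a fixed lag after an event whose date depends on the assigned arm and on how many sessions the patient has. A centre that follows the schedule exactly will not hold a 3-month scan for patients in general. A centre that tries to honour the outcome line has to choose its own origin and date.

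Two consequences follow from tying the scan to the last session.

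- The arms are read at different times after PCNL. This matters because the Introduction itself argues that residual fragments change with time after PCNL: they may embed or encrust, and delay may permit growth.
- A patient who is randomised but receives no ESWL has no last session, and therefore no scheduled outcome scan.

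At stake is whether the primary endpoint, as stated, can be obtained from the scheduled data. A scan that was not taken on the right date cannot be recovered at analysis.

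**Working it through.** The plan gives no scan date of its own to reproduce, so the check derives the dates from the written schedule.

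**Inputs**
- First ESWL, Group A: day 7–14 after PCNL (Randomization).
- First ESWL, Group B: day 21–28, from "ESWL after 3–4 weeks". PCNL is assumed as the origin, as in Group A.
- Sessions, k: 1 to 3 (ESWL Protocol).
- Interval between sessions, d: not stated; 7 to 28 days is assumed as a range.
- Lag from last session to scan: 14 days (Follow-Up).
- 3 months: 13 weeks × 7 = day 91.

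**Formula**

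Scan day after PCNL = first ESWL day + (k − 1) × d + 14.

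**Origin = PCNL**

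One session needs no assumption about d:
- Group A: 7 + 14 = 21 to 14 + 14 = 28. Shortfall: 91 − 28 = 63 to 91 − 21 = 70 days, or 9–10 weeks.
- Group B: 21 + 14 = 35 to 28 + 14 = 42. Shortfall: 91 − 42 = 49 to 91 − 35 = 56 days, or 7–8 weeks.

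Three sessions, by assumed interval:

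| Interval d | Group A scan day | Group B scan day |
|---|---|---|
| 7 days | 35–42 | 49–56 |
| 14 days | 49–56 | 63–70 |
| 21 days | 63–70 | 77–84 |
| 28 days | 77–84 | 91–98 |

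For a third-session scan to fall on day 91, the last session must be on day 91 − 14 = 77. The interval would then have to be (77 − 14)/2 = 31.5 to (77 − 7)/2 = 35 days in Group A, and (77 − 28)/2 = 24.5 to (77 − 21)/2 = 28 days in Group B. Some patients could meet this by chance, but nothing schedules it.

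**Other origins**
- Last ESWL session: the scan is at day 14 for every treated patient, 91 − 14 = 77 days (11 weeks) early.
- First ESWL session: the scan is at (k − 1) × d + 14. That is day 14 for one session, and 2 × 28 + 14 = day 70 for three sessions 28 days apart.
- Randomisation: its date relative to PCNL is not given. Eligibility requires residual stones on postoperative imaging, so randomisation cannot precede PCNL. Counted from randomisation, each scan falls no later than the PCNL-based day above, so a one-session patient is at least as far from 3 months.

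**Difference between arms (same k, same d)**

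The terms (k − 1) × d and 14 cancel, which leaves the difference in first ESWL day.
- Matching window points: 21 − 7 = 14 and 28 − 14 = 14 days.
- Extremes: 21 − 14 = 7 and 28 − 7 = 21 days.

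Group B is therefore scanned about 14 days later after PCNL (range 7–21), and the two windows do not overlap. Time from last session to scan is 14 days in both arms.

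**The case against.** The best reply is that in so short a protocol the 2-week scan may be meant only as a check after treatment, with a 3-month assessment implied by the outcome line. This is a possible reading, and it stands to this extent: the documents do not establish that the trial will report a 2-week rate under a 3-month label. They do establish that the two lines are unreconciled. The stone-free definition is attached to the 2-week scan, no 3-month scan is listed, and the origin is missing. A statistical analysis plan can set windows and handle missing data, but it would not normally add an imaging visit that the protocol's follow-up does not contain.

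A second reply is that the 2-week rule treats the arms fairly in one respect, because time since the last session is the same in both. That is correct. A reader might infer that Group B simply gets longer for fragments to clear after treatment. The schedule does not support this: only time since PCNL differs.

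The third reply is that a fixed date from PCNL has an imbalance of its own. This also stands. At day 90, a one-session patient in Group A is 90 − 14 = 76 to 90 − 7 = 83 days past ESWL, and one in Group B is 90 − 28 = 62 to 90 − 21 = 69 days past it. That difference of about 2 weeks is part of comparing two timing strategies. It is also a reason to state the choice openly, and to accept a 2-week primary endpoint as a legitimate alternative if it is named as such.

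**Conclusion.** The point holds as a contradiction inside the Protocol that has to be resolved. No choice of origin makes the scheduled scan a 3-month scan for patients in general, so following the schedule as written does not deliver the stated primary endpoint.

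Its size depends on the reading. For one-session patients with PCNL as the origin in both arms, the scan is about 7–10 weeks early. Counted from the last session, it is 11 weeks early for everyone. With more sessions the shortfall from PCNL shrinks, and with three sessions at an assumed 28 days it disappears in Group B. The lag of about 14 days between arms (range 7–21) assumes the same number of sessions, the same interval, and PCNL as Group B's origin.

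Three further inferences are tempting, and the documents do not support them:
- **Loss of power.** A reader might infer that the stone-free rate at 2 weeks is lower than planned and the trial underpowered. The calculation is set "to detect a 10% difference in stone-free rate (SFR) between groups" around a prior rate of 93–95%, but the time point of that prior rate is not given, nor is any 2-week rate. This point changes no sample size.
- **More missing outcomes in Group B.** Patients without ESWL have no scheduled scan in either arm. Nothing shows that they will be more frequent in the arm that waits.
- **Sessions driven by response.** The Protocol gives only the maximum, not the rule for repeating a session.

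**What to change.** Reconcile the outcome line with the imaging schedule by amendment, before outcome scans are taken.

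- Name one origin common to both arms, for example the date of PCNL, and state the origin of Group B's treatment window so that the dates can be computed.
- Schedule the primary-outcome imaging at 3 months from that origin, e.g. day 90 ± 7, for every randomised patient, whatever number of ESWL sessions was given, including none.
- Analyse by assigned group.
- Keep the 2-week scan as a treatment check or a secondary outcome, and attach the stone-free definition explicitly to the primary scan.

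If the sponsor intends the 2-week scan to be primary, the outcome line should instead be restated as the stone-free rate two weeks after the last session, with a dated scan specified for patients who receive no ESWL.

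The cost of the first option is a short amendment, tracking patients to a fixed date, and one scan that the stated endpoint already implies. Its downside is that the delayed arm has about 2 weeks less time after ESWL at assessment; the amendment should say that this belongs to the comparison of strategies. The second option needs no extra scan for treated patients, but it gives up the 3-month endpoint and keeps the difference between arms in time since PCNL.
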